## ***COVID19***

COVID19 related TEAEs will be analyzed using selection defined in [Section 2.1.4.1](#) and will be presented by SOC and PT.

## ***Overdose***

A listing of patients who reported overdose during the study will be provided. This listing will include drug with overdose.

## ***Neutropenia and neutropenic complications***

Neutropenia (from laboratory abnormalities) will be displayed along with febrile neutropenia and neutropenic infections (see [Section 2.1.4.1](#)).

Duration of Grade 3/4 neutropenia episode, cumulative duration of Grade 4 neutropenia by patient and time to first Grade 3/4 neutropenia will be analyzed using laboratory data.

The start date of a Grade 4 laboratory neutropenia episode is defined as the date of first Grade 3/4 assessment for that episode. The end date of a Grade 4 neutropenia episode is defined as the first date of neutropenia assessment afterwards of Grade 0/1/2 for that episode assuming there will be at least 3 days between the first Grade  $\leq 2$  neutropenia and the next Grade  $\geq 3$  assessment (if any). If the start date of a new episode is within 3 days of the previous episode, then the two episodes will be considered as one episode. The worst grade of an episode is the worst grade of all assessments included in that episode.

Duration of a Grade 3/4 neutropenia episode (in days) is defined as end date of an episode – start date of an episode +1. If a patient does not have an end date before the cutoff date in an episode then the duration of the episode will be censored at the last neutrophil assessment of Grade 3/4 or the cutoff date, whichever comes first.

Time to first Grade 3/4 neutropenia (in days) is defined as: date of the first on-treatment Grade 3/4 neutropenia assessment – date of first treatment +1. If a patient does not have Grade 3/4 neutropenia, time to first Grade 3/4 neutropenia will be censored at the last assessment of neutropenia of Grade 0/1/2 or the cutoff date, whichever comes first. If a patient does not have any on-treatment assessment of neutropenia, then the patient will be censored at Day 1.

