8.2.3.4 Dose adjustments in Pd arm

Dose adjustments for patients treated with pomalidomide and dexamethasone combination in the case of hematological toxicity are shown in Table 5.

Table 5 - Guidelines for dose adjustments for hematologic toxicities - pomalidomide/dexamethasone combination

Adverse event	Recommended action	
	Dexamethasone ^a	Pomalidomide
Platelets		
Thrombocytopenia Grade 3 without bleeding	
Day 1 of cycle: delay until improvement $\geq 50 \times 10^9/L$^b and administer at same dose level^c
 
Within cycle: maintain full dose of study treatment as planned
	
Thrombocytopenia Grade 4 with or without bleeding	
Day 1 of cycle: delay Day1 administration until improvement $\geq 50 \times 10^9/L$^b and administer at the same dose level^c
 
Within cycle: maintain full dose of study treatment as planned
 
Further episodes: same recommendations
	
Day 1 of cycle: delay Day 1 administration until recovery and decrease pomalidomide by one dose level^c
 
Within cycle: hold pomalidomide until bleeding is controlled and platelet recover $\geq 50 \times 10^9/L$, and then re-start with 1 dose level decrease up to planned Day 21. Next cycle will be re-started with this one dose level decrease
 
Second episode: same recommendation with decrease of pomalidomide by a second dose level
 
Third episode: discontinue pomalidomide

Adverse event	Recommended action	
	Dexamethasone ^a	Pomalidomide
Neutropenia		
Neutropenia Grade 3 (≥ 0.5 and $< 1.0 \times 10^9/L$)	Day 1 of cycle: delay until recovery $\geq 1.0 \times 10^9/L$ and administer at same dose level ^a Within cycle: maintain the same dose level as planned	

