10.1.3 Treatment period

10.1.3.1 Cycle 1 (Day 1, Day 8, Day 15 and Day 22 all ± 1 day)

The following procedures are to be performed/assessed/completed **within 24 hours prior to the start of study treatment on Day 1 in both arms unless specified otherwise:**

- Physical examination to be performed within 24 hours prior to study treatment administration: main diagnoses to be reported in the eCRF as AEs and newly occurring laboratory abnormalities to be recorded in laboratory pages.
- Vital signs including blood pressure, heart rate and body temperature on D1, D8, D15, and D22. In addition in IPd arm, prior to start of each isatuximab infusion, 1 hour after start of each infusion and at the end of each infusion.
- ECOG PS on D1, D8, D15, and D22.
- Study treatment administration.
- ePROs (EORTC QLQ-C30, MY20 and EQ-5D-5L).
- All AEs/SAEs throughout the cycle.
- Concomitant medications from randomization and used throughout the cycle.
- Second primary malignancies.

- Patient diaries for oral study treatment (dexamethasone when taken orally and pomalidomide; except for study treatment doses administered by the study nurse/doctor).
- Contraception and counselling for FCBP and partner (Day 1).
- Thromboprophylaxis as described in [Section 8.9.1](#).

Local laboratory assessments

- Pregnancy test (urine or serum; with a minimum sensitivity of 25 mIU/mL) to be performed and results available on Day 1 within 24 hours prior to study treatment start and then weekly (independently of treatment delay/hold) for FCBP.
- Blood chemistry to be assessed within 24 hours prior to study treatment administration on Day 1, Day 8, Day 15, and Day 22: SGOT (AST), SGPT (ALT), bilirubin (total and direct), alkaline phosphatase, lactate dehydrogenase (LDH), sodium, potassium, chloride, bicarbonate/carbon dioxide, calcium, corrected serum calcium, magnesium, phosphate, uric acid, serum creatinine and estimated creatinine clearance (MDRD Formula), urea or BUN, fasting glucose (according to site guidelines), albumin and total protein.
- Hematology, to be assessed weekly within 24 hours prior to study treatment administration on Day 1, Day 8, Day 15, and Day 22: hemoglobin, hematocrit, RBC, WBC with differential (including ANC), and platelet count. If G4 neutropenia, assess ANC every 2-3 days until $ANC \geq 0.5 \times 10^9/L$ and at least weekly thereafter until $ANC \geq 1.0 \times 10^9/L$.

Central and local laboratory disease assessment

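### The SAP gives Grade 3/4 episode dates the label Grade 4 and has no separate rule for the planned cumulative duration of Grade 4 neutropenia

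*SAP*

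**What the plan says.** The relevant text is SAP 2.4.5.1, under the heading Neutropenia and neutropenic complications. It lists the outputs: "Duration of Grade 3/4 neutropenia episode, cumulative duration of Grade 4 neutropenia by patient and time to first Grade 3/4 neutropenia will be analyzed". Grade 3/4 episode duration and cumulative Grade 4 duration are thus separate quantities.

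The episode rules follow:

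- Start: "The start date of a Grade 4 laboratory neutropenia episode is defined as the date of first Grade 3/4 assessment for that episode".
- End: "The end date of a Grade 4 neutropenia episode is defined as the first date of neutropenia assessment afterwards of Grade 0/1/2 for that episode". A gap condition follows, under which episodes separated by no more than a few days are merged; it is expressed in terms of Grade 2 or lower and Grade 3 or higher.
- Label: "The worst grade of an episode is the worst grade of all assessments included in that episode".
- Duration: "Duration of a Grade 3/4 neutropenia episode (in days) is defined as end date of an episode – start date of an episode +1". An episode with no end date is censored at the last Grade 3/4 value or the cut-off, whichever is earlier.

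No other text fills the gap. SAP 2.4.5.3 mentions duration for the haematological abnormalities but does not define it. Table 10 in SAP section 3 names time to first Grade 3/4 neutropenia and duration of Grade 3/4 neutropenia, and does not name the Grade 4 quantity.

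**The concern.** The two date sentences speak of a Grade 4 episode but use Grade 3/4 boundaries. A Grade 3 value can open the episode, and improvement from Grade 4 to Grade 3 does not close it. A programmer asked for "cumulative duration of Grade 4 neutropenia by patient" would find only these dates, and summing them would give the length of the whole Grade 3/4 episode under a Grade 4 heading.

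The distinction has content in this trial. The protocol separates the grades at a neutrophil count of 0.5 x 10^9/L and gives different within-cycle guidance for pomalidomide in the two grades (Protocol Tables 3 and 5). Neutropenia is also common with this combination: Grade 3-4 laboratory neutropenia was reported in 85.7% of patients in the Phase 1b study (Protocol 4.4.2.2.2 and 4.5.3). A Grade 4 duration that contains Grade 3 time would describe this toxicity as more severe than it was.

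**Working it through.** The plan states no figure for this quantity, so there is none to reproduce. The check applies the written dates and a Grade 4-only rule to the same values.

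**Inputs from the documents**

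- Written boundaries and the end minus start plus 1 formula: SAP 2.4.5.1.
- Grade 3 is a count of at least 0.5 and below 1.0 x 10^9/L; Grade 4 is below 0.5: Protocol Tables 3 and 5.
- Sampling after a Grade 4 value: every 2-3 days until the count reaches 0.5, then at least weekly until it reaches 1.0 (Protocol 1.2 footnote m, 10.1.3.1 and 10.1.3.2). The first threshold ends Grade 4 and the second ends Grade 3, so the data can separate the grades.

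**Formulas**, for an episode with one run of Grade 4 values. Let s34 be the day of the first Grade 3/4 value, s4 the first Grade 4 value, e4 the first later value below Grade 4, and e34 the first later value of Grade 2 or lower.

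- Written dates: e34 - s34 + 1
- Grade 4 only, same plus-1 convention: e4 - s4 + 1
- Excess: (s4 - s34) + (e34 - e4)

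The excess cannot be negative. It is positive when Grade 3 values precede or follow the Grade 4 run, and zero when there are none.

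**Hypothetical series.** These are assumptions, chosen to fit weekly Cycle 1 visits and the closer sampling after Grade 4.

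| Series | Written dates | Grade 4 only | Excess |
|---|---|---|---|
| G4 Day 15, G3 Day 18, G2 Day 25 | 25 - 15 + 1 = 11 | 18 - 15 + 1 = 4 | 0 + 7 = 7 |
| G3 Day 8, G4 Days 15 and 17, G3 Days 20 and 27, G2 Day 34 | 34 - 8 + 1 = 27 | 20 - 15 + 1 = 6 | 7 + 14 = 21 |
| G4 Days 15 and 17, G2 Day 20 | 20 - 15 + 1 = 6 | 20 - 15 + 1 = 6 | 0 |

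**Grade 3 only.** With Grade 3 on Days 8, 15 and 22 and Grade 2 on Day 29, the total is 0 days if only episodes whose worst grade is 4 are summed. If every episode that meets the start and end sentences is summed, it is 29 - 8 + 1 = 22 days. The SAP does not say which.

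**The case against.** The strongest reply is that Grade 4 in the two date sentences is a slip for Grade 3/4. The duration formula, the gap condition, the worst-grade label and the censoring rule all describe Grade 3/4 episodes, so this is a natural reading. It stands as a limit on the claim: a reader might infer that the cumulative Grade 4 duration is certainly overstated, but the SAP never writes out how that quantity is summed. It does not remove the problem, because on this reading a planned output has no definition at all.

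The second reply concerns impact, and most of it stands. SAP 2.4.5 makes the safety analysis essentially descriptive. Neutropenia severity is also shown by worst laboratory grade and by shift tables (SAP 2.4.5.3), and febrile neutropenia and neutropenic infections are reported separately; none of these uses the episode dates. A reader might infer that the comparison between arms is distorted. The same rule applies to both arms, and the documents contain nothing on how Grade 3 and Grade 4 time is split in each, so neither a distortion nor its direction is shown.

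A reader might also infer that patients who never reach Grade 4 are credited with Grade 4 days. The worst-grade sentence points the other way, although its use as a filter is not stated.

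**Conclusion.** The text needs correcting on either reading. Taken literally, the written dates count Grade 3 days as Grade 4; taken as a slip, they leave the cumulative Grade 4 duration undefined.

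An overstatement follows only if these dates are used for the Grade 4 sum, and only in patients whose Grade 4 episode has Grade 3 values before or after the Grade 4 run. The excess of 7 and 21 days in the examples shows the mechanism and is not an estimate for the trial, whose actual size cannot be obtained from the documents.

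The point is minor. It concerns one descriptive safety summary and leaves PFS, ORR, OS, the error rate and the sample size untouched.

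**What to change.** 1. In SAP 2.4.5.1, relabel the existing start and end dates as those of a Grade 3/4 episode.
2. Add a Grade 4 period: it opens at the first Grade 4 value and closes at the first later value of Grade 3 or lower. Give it its own gap-merging rule. Censor an open period at the last Grade 4 assessment or the cut-off date, whichever is earlier. Sum the periods per patient.
3. Name the cumulative Grade 4 duration in Table 10. That table confines time to first and duration of Grade 3/4 neutropenia to the primary PFS analysis and carries other neutropenia outputs on to the later OS analyses, so the timing of the Grade 4 summary is unclear.
4. Check which derivation was used for any table already produced. SAP version 3 postdates the primary analysis (SAP 1.6, Table 1), so this output may already exist.

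The cost is a few sentences and a small programming change, plus the re-run of one descriptive table if the written dates were used for it. No new data are needed.

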## ***Respiratory TEAEs***

Respiratory TEAEs will be analyzed using selection defined in [Section 2.1.4.1](#) and will be presented by PT.

### ***Thrombocytopenia and hemorrhages***

The number (%) of patients will be provided for:

- On-treatment thrombocytopenia (Lab) identified through grading of laboratory data per the NCI-CTCAE 4.03, by grade
- Hemorrhages as defined in [Section 2.1.4.1](#) by grade
- Hemorrhages following Grades 4 thrombocytopenia (Lab). The first hemorrhages event occurring within 8 days after any occurrence of the thrombocytopenia (Lab) will be used for this analysis.

### ***Hemolytic disorders***

Hemolytic disorders that occurred within 8 days after the blood cell transfusion will be analyzed using selection defined in [Section 2.1.4.1](#) and will be presented by PT.

A listing of patients with hemolytic disorders will be provided. This listing will include the PT, study day of diagnosis (from first dose of study treatment), interval to onset from the last study treatment before the diagnosis (last drug administered), duration of AE, the cycle of occurrence, severity, seriousness, outcome, action taken on study treatment, study day of the blood transfusion, and results and sampling date of indirect anti-globulin test.

### ***Autoimmune disorders***

A listing of patients with autoimmune disorders (selected using definition in [Section 2.1.4.1](#)) will be provided. This listing will include the PT, study day of diagnosis (from first dose of study treatment), interval to onset from the last study treatment before the diagnosis (last drug administered in a combination treatment), duration of AE, the cycle of occurrence, severity, seriousness, action taken on study treatment, and outcome.

### ***TLS***

A listing of patients with TLS reported in eCRF AE forms during the study will be provided.

### ***Exposure-adjusted analyses of TEAEs***

The event rate per patient-year (the number of patients with an event divided by total patient-years) will be provided by SOC and PT for the most frequent ( $\geq 5\%$  of patients in any group) TEAEs, most frequent ( $\geq 5\%$  of patients in any group) Grade  $\geq 3$  TEAEs, serious TEAEs, TEAE leading to definitive discontinuation and AEs leading to death in context other than disease progression (see definition in [Section 2.4.5.2](#)). For a patient with event, patient year is censored at time of first event; for patient without event, it corresponds to length of treatment period as defined in [Section 2.1.4](#).

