### ***Observation period***

The observation period starts from the time when the patient gives informed consent and is divided into 3 periods:

- The **pre-treatment** period is defined as the time from the signed informed consent date up to the first dose of study treatments.
- The **treatment** period is defined as the time from the first dose of study treatments administration to the last dose of study treatments + 30 days.
- The **post treatment** period is defined as the period of time starting the day after the end of the treatment period up to the end of the study (as defined in the protocol).

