##### **Adverse event observation period**

- Pre-treatment adverse events are defined as any adverse event reported during the pre-treatment period.
- Treatment-emergent adverse events (TEAEs) are adverse events that developed or worsened or became serious during the treatment period.
- Post-treatment adverse events are adverse events that developed or worsened or became serious during the post-treatment period.

All AEs (including SAEs and AESI) will be graded according to National cancer institute common terminology for adverse events (NCI-CTCAE) v4.03 and coded to a lower-level term (LLT), preferred term (PT), high-level term (HLT), high-level group term (HLGT) and associated primary system organ class (SOC) using the version of Medical Dictionary for Regulatory Activities (MedDRA) currently in effect at Sanofi at the time of database lock.

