#### **2.4.5.2 Deaths**

An overview of Grade 5 AEs will be provided summarizing number (%) of patients with any:

- Grade 5 AE (TEAE and post-treatment).
- Fatal TEAE (regardless date of death/period).
  - Grade 5 TEAE with a fatal outcome during the treatment period,
  - Any Grade TEAE with a fatal outcome during the post-treatment period.
- Post-treatment Grade 5 AE (excluding a TEAE that worsened to Grade 5 during the post-treatment period).

The following summaries of deaths will be generated for the safety population.

- Number (%) of patients who died by study period (on-treatment, post-treatment, within 60 days of first dose) and reasons for death (disease progression, AE, other) by treatment received.
- Listing of deaths in non-randomized patients or randomized but not treated patients (this listing will be generated on the screened patients).
- All TEAEs leading to death by primary SOC and PT, sorted by the internationally agreed SOC order and by decreasing incidence of PTs.
- All TEAEs related to treatment and leading to death by primary SOC and PT sorted by the internationally agreed SOC order and by decreasing incidence of PTs.
- Number (%) of patients with TEAE(s) leading to death regardless of relationship and related to IMP by Primary SOC, HLGT, HLT and PT.
- Summary of AEs leading to death, by Primary SOC and PT
  - In context of disease progression (death within 30 days from last study treatment administration and the cause of death is disease progression),

- In context other than disease progression (death within 30 days from last study treatment administration and for whom cause of death is not disease progression or the death occurred more than 30 days from last study treatment administration and the cause of death is adverse event).

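### The exposure-adjusted rate for fatal AEs outside disease progression counts deaths after the treatment period but leaves out event-free patients' time after it, so the rate is biased upward

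*SAP*

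**What the plan says.** SAP 2.4.5.1 (Exposure-adjusted analyses of TEAEs) defines the rate as "the number of patients with an event divided by total patient-years". It lists frequent TEAEs, frequent Grade 3 or higher TEAEs, serious TEAEs, TEAEs leading to definitive discontinuation, and "AEs leading to death in context other than disease progression". For the last item it refers to 2.4.5.2 for the definition.

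SAP 2.4.5.2 gives that definition two branches. One is death within 30 days of the last administration with a cause other than progression. The other is that "the death occurred more than 30 days from last study treatment administration and the cause of death is adverse event". The second branch has no upper time limit.

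Time at risk is set in 2.4.5.1. Someone who has the event contributes time up to its first occurrence. The rule for everyone else is: "for patient without event, it corresponds to length of treatment period as defined in". The reference is to 2.1.4, and there the treatment period is "the time from the first dose of study treatments administration to the last dose of study treatments + 30 days".

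TEAEs are "adverse events that developed or worsened or became serious during the treatment period" (SAP 2.1.4.1), so the four TEAE categories are confined to the same window as their person-time.

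**The concern.** A rate needs events and time at risk from the same window. Here a fatal AE arising six months after the last dose adds one to the numerator. A patient alive and event-free over the same six months adds nothing to the denominator for those months. The result is not an incidence rate for the treatment period or for follow-up, and it is too high against either.

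The SAP history (Table 1, version 2) says the exposure-adjusted analyses were added to characterise safety better and in response to regulatory comments. Their purpose is to compare arms with different time on treatment. Fatal AEs without progression are a sensitive comparison in an open-label add-on trial, and the counts are likely to be low enough for a few mismatched deaths to move the rate.

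**Working it through.** **Plan's own figures.** The documents give no exposure-adjusted rate to reproduce, so the check is on the planning assumptions used below. Events for HR 0.60, one-sided 0.025, 90% power, 1:1 allocation: 4 × (1.960 + 1.282)² / (ln 0.60)² = 42.03 / 0.2609 = 161.1, rounded up to 162. This matches Protocol 11.1.

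**Inputs from the documents.** Median PFS 4 and 6.67 months, median OS 13 and about 19 months (13/0.685), exponential, 15 patients per month (Protocol 11.1); treatment until progression, unacceptable AE or patient wish (Protocol 6.1); treatment period to last dose + 30 days (SAP 2.1.4).

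**Assumptions, not in the documents.** Treatment stops at the PFS event. The on-treatment fatal-AE rate is 0.06 per patient-year in both arms; it sets the scale and hardly affects the ratios. The fatal-AE risk after the treatment period is ρ times the on-treatment risk, with ρ from 0 to 1.

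**Model check.** At 18 months the model gives about 168 PFS events and 84 deaths, against the plan's 162 events and its 80-death scenario. At 43 months it gives about 227 deaths against the planned 198, so the later figures are only illustrative.

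**Mean time per patient (months).**

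| Cut-off | Arm | Treatment period | Follow-up | Post-treatment | Post / treatment |
|---|---|---|---|---|---|
| 18 | Pd | 4.45 | 6.69 | 2.25 | 0.505 |
| 18 | IPd | 5.61 | 7.31 | 1.71 | 0.305 |
| 43 | Pd | 6.42 | 15.39 | 8.97 | 1.398 |
| 43 | IPd | 9.85 | 18.96 | 9.11 | 0.925 |

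**Formula.** To first order, inflation = 1 + ρ × (post-treatment / treatment time).
- 18 months, ρ = 0.25: Pd 1 + 0.25 × 0.505 = 1.13; IPd 1 + 0.25 × 0.305 = 1.08.
- 18 months, ρ = 1: Pd 1.51; IPd 1.31 (1.505 and 1.305 before rounding).

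This slightly overstates the effect, because patients with a late event contribute their own time up to that event. Simulating the rule as written gives:

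| Cut-off | ρ | Pd | IPd | IPd/Pd (true value 1) |
|---|---|---|---|---|
| PFS | 0.25 | ×1.12 | ×1.07 | 1.07/1.12 = 0.96 |
| PFS | 1 | ×1.47 | ×1.28 | 1.28/1.47 = 0.87 |
| 43 months | 0.25 | ×1.33 | ×1.22 | 1.22/1.33 = 0.92 |
| 43 months | 1 | ×2.19 | ×1.82 | 1.82/2.19 = 0.83 |

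With ρ = 0 there is no inflation against the on-treatment rate.

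**Number of late deaths.** Per 150 patients at ρ = 0.25: 150 × (0.06/12) × 0.25 × 2.25 = 0.4 (Pd) and × 1.71 = 0.3 (IPd) at 18 months; × 8.97 = 1.7 and × 9.11 = 1.7 at 43 months.

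**When the arm difference reverses.** To first order, inflation is equal when ρ in IPd is 0.505/0.305 = 1.66 times ρ in Pd at 18 months, or 1.398/0.925 = 1.51 times at 43 months. Beyond that, IPd is inflated more. For example, ρ of 0.10 (Pd) and 0.20 (IPd) gives ×1.05 and ×1.06 at 18 months. Unequal stopping for reasons other than progression has the same effect: added hazards of 0.02 (Pd) and 0.10 (IPd) per month with ρ = 0.25 give ×1.14 and ×1.18.

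**The case against.** **The subsection is headed TEAEs, so late deaths may not be intended.** This does not remove the mismatch. The item itself says AEs and points to a definition that names deaths beyond 30 days. SAP 2.4.5.2 lists TEAEs leading to death as a separate summary, so the plan distinguishes the two.

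**The time of first event may mean AE onset.** The SAP does not say whether it means onset or death. If onset, a late death from an AE that began on treatment is matched, and only AEs starting after the window are mismatched. This narrows the problem but does not close it.

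**Few late events will be collected.** This stands as a limit on size. Under Protocol 10.4.2, new AEs after 30 days are reported only if treatment-related, although second primary malignancies are followed to the end of the study. A late death must also have an AE as its cause, which is narrower than the within-30-day test of any cause other than progression. Full on-treatment risk persisting indefinitely (ρ = 1) is therefore an upper bound.

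**The consequence is limited.** This also stands. SAP 2.4.5 describes the safety analyses as essentially descriptive, no decision rule uses this rate, and 2.4.5.2 tabulates deaths by period and reason. In SAP Table 10 the exposure-adjusted row shows no mark under either analysis. That may be a conversion loss, but it leaves the timing unclear.

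**A reader might infer that the control arm is always inflated more, so the table favours IPd.** The documents do not support this as a general statement. It needs a similar late-to-on-treatment risk ratio in both arms and treatment time that tracks planned PFS. Neither is given, and treatment also stops for AEs and patient wish.

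**Conclusion.** The mismatch is certain from the text. Following SAP 2.4.5.1 as written gives an upward-biased rate for this one category whenever a counted event falls after the treatment period.

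The size is conditional. It rests on planned PFS as a proxy for time on treatment, an equal assumed on-treatment rate, and ρ between 0.25 and 1. Under those assumptions the inflation is about 12% to 47% (Pd) and 7% to 28% (IPd) at the PFS cut-off, and 33% to 119% and 22% to 82% at 43 months. Only if ρ is also similar in the two arms does the distortion favour IPd, with a ratio of 0.96 to 0.87 and then 0.92 to 0.83.

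Higher rates, such as 0.101 and 0.086 at the PFS cut-off with ρ = 1, come from adding a separate death hazard to the PFS hazard. Planned PFS already includes death; used directly, it gives about 0.089 and 0.077.

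The rule should be corrected. It does not bear on the efficacy conclusions or on any formal test.

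**What to change.** Amend the last sentence of the subsection in SAP 2.4.5.1 in one of two ways.

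1. Restrict this category to fatal AEs with onset in the treatment period, with person-time to onset or to the end of the treatment period.
2. Keep all deaths that meet the 2.4.5.2 definition, use time from first dose to death, last contact or cut-off for every patient, and label the result a follow-up-adjusted rate.

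In either case state whether the time of first event is AE onset or death, and mark in Table 10 at which analyses the table is produced.

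The cost is one SAP sentence, one Table 10 entry and a small programming change. Under the first option fewer fatal events appear in this one table; they remain visible in the 2.4.5.2 death summaries.
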